4. STUDY DESIGN

4.1. Overall Design

Study ARGX-113-2211 is a long-term, single-arm, open-label, multicenter extension of pSS-qualifying efgartigimod studies designed to evaluate the long-term safety of efgartigimod in adult patients with pSS. Participants will be enrolled from both active and placebo arms of qualifying efgartigimod studies and receive efgartigimod IV 10 mg/kg over 48 weeks in the extension study without knowledge of their treatment assigned in the qualifying study. To be eligible to enroll in this study, participants must have completed the treatment period of the qualifying study and must not have permanently discontinued the IMP in that study.

Participants will receive efgartigimod 10 mg/kg by IV infusion either Q2W or QW. The dosing regimen is based on whether the participant is a responder or nonresponder on day 1. Participants will be considered as responders if they have a reduction in clinESSDAI score of ≥ 3 points from baseline (ie, the final visit of a previous qualifying study) and/or a change in score that reclassifies their disease from moderate severity (clinESSDAI ≥ 5) to mild severity (clinESSDAI < 5). Participants will be considered as nonresponders if they do not have a reduction in clinESSDAI score of ≥ 3 points from baseline and/or did not reach a clinESSDAI < 5 . ClinESSDAI assessments to determine responder status using the baseline will be conducted on day 1 and weeks 16 and 24. Responders will receive IV infusions Q2W. Nonresponders will receive an infusion QW until such time that they are considered to be responders. If a participant is not a responder at week 24, they will be evaluated by the PI for therapeutic failure:

- Therapeutic failure - the participant will discontinue study treatment
- Not a therapeutic failure - the participant will continue QW dosing regimen. ClinESSDAI will be conducted at weeks 32, 36, 40, and 44 until confirming responder status and switching to Q2W dosing regimen. The PI will continue to evaluate the participant for therapeutic failure

If the participant and/or investigator consider there to be a reduction in therapeutic effect once the patient has switched to Q2W, the participant will return for an unscheduled visit during which a clinESSDAI, a blood sampling for PK and ADA will be collected.

If there has been an increase in clinESSDAI score of ≥ 3 points and/or a change in score that reclassifies their disease from mild severity to moderate severity the participant will revert to QW dosing regimen and will remain on this dose regimen for the remainder of the treatment period.

IMP infusions must occur at the site for a minimum of 3 consecutive visits (for QW dosing regimen: baseline visit and the week 1 and 2 visits; for Q2W dosing regimen: baseline visit and the week 2 and 4 visits) before home infusions are allowed. If doses are missed at 1 or more of these visits, then dosing at subsequent visits will also be on-site. IMP administration at home will not commence until after 3 consecutive doses have been administered on-site.

Participants will return for a follow-up visit approximately 56 days after the final IMP administration.

The study's primary objective is to assess the long-term safety of efgartigimod in participants with pSS. The primary outcome of this study will be the incidence and severity of AEs and AESIs, the incidence of SAEs, changes in laboratory test results, vital signs, and ECG results. Additional assessments will be conducted, and blood samples will be collected to assess the effectiveness of efgartigimod at treating pSS, the PD effect of efgartigimod, and the immunogenicity of efgartigimod. Blood samples will also be collected to monitor the concentration of efgartigimod in blood over time.

A minimum of 10 study site visits over the 48-week treatment period and 56-day follow-up period are planned (baseline, weeks 1 [for QW regimen], 2, 4, 8, 12, 16, 24, 36, 48, and the SFV); all other visits (except for the first 3 consecutive visits) may be conducted by home health care service, or telemedicine visits.

The maximum length of time a participant can be in the study is approximately 56 weeks (48 weeks treatment plus 8 weeks of follow-up).

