ARGX-113-2211 is a long-term, single-arm, open-label, multicenter extension study of the pSS-qualifying efgartigimod studies designed to evaluate the long-term safety of efgartigimod in adult patients with pSS. Participants will be enrolled from both active and placebo arms of qualifying efgartigimod studies and receive efgartigimod 10 mg/kg over 48 weeks in the extension study without knowledge of their treatment assignment in the qualifying study. Eligible participants must have completed the treatment period of the qualifying study and must not have permanently discontinued the IMP in that study.

Brief Summary:

Participants will receive efgartigimod 10 mg/kg by IV infusion either Q2W or QW. The dosing regimen is based on whether the participant is a responder or nonresponder. Responder status will be determined by clinESSDAI assessments conducted on day 1, week 16, and week 24 and using the baseline of the qualifying study. Participants who are not responders at week 24 will be evaluated by PI for therapeutic failure. If a participant is a therapeutic failure, they will discontinue study treatment. If a participant is not a therapeutic failure, they will continue QW dosing regimen, and a clinESSDAI will be conducted at weeks 32, 36, 40, and 44 until confirming responder status and switching to Q2W dosing regimen. The PI will continue to evaluate the participant for therapeutic failure.

The study's primary objective is to assess the long-term safety of efgartigimod in participants with pSS. Additional assessments will be conducted, and blood samples collected to assess the effectiveness of efgartigimod at treating pSS, the PD effect of efgartigimod, and the immunogenicity of efgartigimod. Blood samples will also be collected to monitor the concentration of efgartigimod in blood over time.

Number of Participants:

Up to approximately 30 subjects who have completed the efgartigimod pSS study (ARGX-113-2106) will be enrolled for in the OLE study (ARGX-113-2211).

Note: *Enrolled* means the participant agrees to participate in the clinical study by completing the informed consent process.

[figure not shown]
Study Arms and Duration:

Each participant will participate in the following study periods:

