1.2. Schema

Abbreviations: D = day; IV = intravenous; QW = once weekly; Q2W = every 2 weeks; Wk = week.

^a QW or Q2W dosing regimen depending on responder status. Responders (defined as participants with a decrease in clinESSDAI of ≥ 3 points from baseline of qualifying study or who have a change clinESSDAI score that reclassifies their disease from moderate severity to mild severity) will be switched from QW to Q2W dosing regimen. Nonresponders will remain on QW dosing regimen. Switch points (ie, timepoints where clinESSDAI are conducted to determine responder status) will occur on day 1, week 16, and week 24. If a participant is not a responder at week 24, they will be evaluated by the PI for therapeutic failure. If not considered a therapeutic failure, the participant will continue QW dosing regimen and will return at weeks 32, 36, 40 and 44 for a clinESSDAI assessment until confirming the responder status and switching to Q2W dosing regimen or PI considers the participant to be a therapeutic failure. For QW regimen, the final dose will be administered at week 47. For Q2W regimen, the final dose will be administered at week 46.

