IMP infusion ^m	X ⁿ	X ^{o,p}																	
AE review	Continuous monitoring																		
Concomitant medications review	Continuous monitoring																		

	BL ^a	Study week																EDV ^b	SFV ^c
		1	2	3	4	5-7	8	9-11	12	13-15	16	17-23	24	25-35	36	37-47	48		
Study day (±2)	1	8	15	22	29	36-50	57	64-78	85	92-120	127	134-162	169	176-246	253	260-330	337		393

BL = baseline; clinESSDAI = clinical; ESSDAI; D = day; d/c = discontinuation; ECG = electrocardiogram; EDV = early discontinuation visit; ESSDAI = EULAR Sjögren’s syndrome disease activity index; ESSPRI = EULAR Sjögren’s Syndrome Patient-Reported Index; EULAR = European Alliance of Associations for Rheumatology; ICF = informed consent form; IgG = immunoglobulin G; IMP = investigational medicinal product; IV = intravenous; MFI = Multidimensional Fatigue Inventory; NA = not applicable; OSS = ocular staining score; PASS = patient acceptable symptom state; PCR = polymerase chain reaction; PD = pharmacodynamics; PGA = patient global assessment; PK = pharmacokinetics; RF = rheumatoid factor; SCR = screening; SFV = safety follow-up visit; SF-36 = 36-Item Short Form Survey; SGUS = salivary gland ultrasonography; SS-A = Sjögren’s syndrome-related antigen A; SS-B = Sjögren’s syndrome-related antigen B; SWSF = stimulated whole salivary flow; UWSF = unstimulated whole salivary flow; W = week.

^a BL will coincide with the final visit of a previous qualifying study. Grayed-out assessments may be conducted as part of the previous qualifying pSS studies.

^b The EDV will be performed within 7 days after last dose administration.

^c Participants will attend a safety follow-up visit 56 ± 3 days after the final IMP administration.

^d Weight mandatory at baseline.

^e Vital signs will be measured before collecting any blood sample or administering IMP infusions.

^f On IMP administration visits, blood samples must be collected predose (preferably within 2 hours before the infusion). On other visits, a blood sample may be collected at any time during the visit.

^h On IMP administration visits, blood samples for PK analyses will be collected predose (preferably within 2 hours before IMP administration). On other visits, a blood sample may be collected at any time during the visit.

ⁱ A PK sample will also be collected within 30 minutes after the end of IMP infusion.

^j The biological domain will remain blinded until the parent study is unblinded.

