8.1. Administrative and Baseline Procedures

The baseline visit for study ARGX-113-2211 will be conducted after the participant has completed the qualifying study. All baseline assessments will be performed before first administration of efgartigimod in ARGX-113-2211, if applicable. Assessments do not need to be repeated if they are performed as part of the last visit of the qualifying study.

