Investigational medicinal product (IMP) infusions must occur at the site for a minimum of 3 consecutive visits (for QW dosing regimen: baseline visit and the week 1 and 2 visits; for Q2W dosing regimen: baseline visit and the week 2 and 4 visits) before home infusions are allowed. If doses are missed at 1 or more of these visits, then dosing at subsequent visits will also be on-site. IMP administration at home will not commence until after 3 consecutive doses have been administered on-site.

[figure not shown]
Participants will return for a follow-up visit approximately 56 days after the final IMP administration.

confidential and proprietary to IQVIA Holdings Inc. and its subsidiaries. Unauthorized use, disclosure or reproduction is strictly prohibited.

A minimum of 10 study site visits over the 48-week treatment period and 56-day follow-up period are planned (baseline, weeks 1 [for QW regimen], 2, 4, 8, 12, 16, 24, 36, 48, and the safety follow-up visit (SFV)); all other visits (except for the first 3 consecutive visits) may be conducted by home health care service, or telemedicine visits. The maximum length of time a participant can be in the study is approximately 56 weeks (48 weeks treatment plus 8 weeks of follow-up).

Figure 1: Study Overview

Abbreviations: D = day; IV = intravenous; QW = once weekly; Q2W = every 2 weeks; Wk = week.

^a QW or Q2W dosing regimen depending on responder status. Responders (defined as participants with a decrease in clinESSDAI of ≥ 3 points from baseline of qualifying study or who have a change clinESSDAI score that reclassifies their disease from moderate severity to mild severity) will be switched from QW to Q2W dosing regimen. Non-responders will remain on QW dosing regimen. Switch points (i.e., timepoints where clinESSDAI are conducted to determine responder status) will occur on day 1, week 16, and week 24. If a participant is not a responder at week 24, they will be evaluated by the PI for therapeutic failure. If not considered a therapeutic failure, the participant will continue QW dosing regimen and will return at weeks 32, 36, 40 and 44 for a clinESSDAI assessment until confirming the responder status and switching to Q2W dosing regimen or PI considers the participant to be a therapeutic failure. For QW regimen, the final dose will be administered at week 47. For Q2W regimen, the final dose will be administered at week 46.

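### Protocol 4.1 measures the ≥3-point clinESSDAI fall that sets the dosing regimen from the extension's own day 1, while the synopsis, schema and SAP figure measure it from the qualifying-study baseline; both glossaries also override the investigator's week-24 judgement

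*Protocol*

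**What the plan says.** Protocol 4.1 gives two ways to be a responder. The first is a "reduction in clinESSDAI score of ≥ 3 points from baseline (ie, the final visit of a previous qualifying study"). The second is "a change in score that reclassifies their disease from moderate severity" (clinESSDAI ≥5) to mild (<5), with no reference visit named. The next sentence describes nonresponders as lacking the 3-point fall and/or not having reached a score below 5.

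Three other places use an earlier reference:

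- Protocol 1.1 (Synopsis): assessments are "conducted on day 1, week 16, and week 24 and using the baseline of the qualifying study".
- Protocol 1.2 (Schema, footnote a): "decrease in clinESSDAI of ≥ 3 points from baseline of qualifying study".
- SAP 3.1 (Figure 1, footnote a): the fall is counted "from baseline of qualifying study or who have a change clinESSDAI score that reclassifies their disease" from moderate to mild.

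The body text of SAP 3.1 refers only to the baseline, without saying which.

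On timing, footnote a of the Schedule of Activities (SoA) states that "BL will coincide with the final visit of a previous qualifying study", and Protocol 8.1 adds: "Assessments do not need to be repeated if they are performed as part of the last visit of the qualifying study". Day 1 is listed as a switch point in the synopsis and the SoA. The on-site dosing rule in 4.1 provides for Q2W from the start ("for Q2W dosing regimen: baseline visit and the week 2 and 4 visits"), and SAP Section 11, Table D, has exposure classes for participants on Q2W from day 1.

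On stopping, the Definitions of Terms in both documents equate therapeutic failure with nonresponse at week 24 and say that such a participant stops treatment. The synopsis, schema, SoA footnote o, Protocol 4.1 and SAP 3.1 (text and figure) have the PI evaluate week-24 nonresponders. Those not judged failures continue QW, with clinESSDAI at weeks 32, 36, 40 and 44.

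**The concern.** This rule is applied to participants in real time, and Protocol 6.6 sends sites to Section 4.1 for changes to the dosing schedule. The two candidate reference visits lie a whole qualifying treatment period apart, since Protocol Section 2 places rollover at week 24 of that study. Two sites that read different sections could dose identical participants differently, and infusions already given cannot be undone at analysis.

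The 4.1 reference also works against the design. A participant who improved in the qualifying study and then holds that improvement shows no further fall. Protocol 4.3 gives the purpose of Q2W as seeing whether less frequent dosing maintains efficacy, so these are participants whom Q2W was meant for. Under 4.1 they can stay on QW and reach the week-24 therapeutic-failure evaluation. If a site followed the glossary there, treatment would stop without any judgement by the PI.

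**Working it through.** The plan gives no figure to reproduce. The check applies each stated rule to the same scores.

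**Notation.** q = clinESSDAI at the qualifying-study baseline, f = score at the final qualifying-study visit, c = score on the decision day.

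- Synopsis and schema rule: q − c ≥ 3, or q ≥ 5 and c < 5.
- Section 4.1 rule: f − c ≥ 3, or the <5 criterion. That criterion can be read as (a) f ≥ 5 and c < 5; (b) q ≥ 5 and c < 5; or (c) c < 5 alone, which the nonresponder sentence suggests.

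**Step 1: day 1.** The extension baseline is the final qualifying visit, so without a repeat c = f and f − c = 0. The 3-point criterion cannot be met. A separate repeat could differ from f, but only by short-term variation in the score.

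**Step 2: improved, still at ≥5.** Assumed scores: q = 14, f = 10, c = 10 on day 1 and at weeks 16 and 24.

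- Synopsis and schema: 14 − 10 = 4 ≥ 3, a responder each time. Any score up to 14 − 3 = 11 qualifies.
- Section 4.1: 10 − 10 = 0 < 3, and 10 is not below 5 under (a), (b) or (c), so a nonresponder each time. The score would have to reach 10 − 3 = 7 or lower.

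On day 1 the same disagreement arises, under every reading, whenever q − f ≥ 3 and f ≥ 5 (hence q ≥ 8).

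**Step 3: infusions for that participant.** Last doses are at week 47 (QW) and week 46 (Q2W), per the schema.

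| Period | QW (4.1) | Q2W (synopsis and schema) |
|---|---|---|
| Before week 16 | weeks 0 to 15: 16 | weeks 0, 2, …, 14: 8 |
| Before week 24 | weeks 0 to 23: 24 | weeks 0, 2, …, 22: 12 |
| Whole study, if each regimen continues | weeks 0 to 47: 48 | weeks 0, 2, …, 46: 24 |

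The last row is an upper case: it assumes that the PI does not stop treatment and that the regimen never changes.

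**Step 4: already below 5 on day 1.** Assumed scores: q = 10, f = c = 2. Synopsis and schema: responder (10 − 2 = 8). Section 4.1: no under (a), yes under (b), yes under (c). The text does not settle this.

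**Step 5: stopping rule.** Under the glossaries a week-24 nonresponder stops. Under the procedural text the PI decides, and some continue QW. Under the glossary wording, the clinESSDAI assessments set aside for week-24 nonresponders at weeks 32, 36, 40 and 44 would have nobody to assess.

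**Step 6: a separate, minor date error.** With study day = 7 × week + 1, week 16 is day 113, as in SAP Table C. The SoA prints day 127, which is 127 − 113 = 14 days late, and the neighbouring ranges are shifted to match. Correct values: weeks 13 to 15 = days 92 to 106; weeks 17 to 23 = days 120 to 162.

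**The case against.** The intended rule can be recovered. The synopsis, schema and SAP figure agree, and the switch-point list, the on-site dosing rule and Table D all presuppose Q2W starters on day 1. The glossary conflict is likewise answered by the procedural sections. Being a nonresponder at week 24 under 4.1 triggers an evaluation, not an automatic stop. All of this stands, and it limits the severity. It does not remove the conflict, because 4.1 is the section to which dosing changes are referred.

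The analysis effects are also indirect. The regimen subgroups in SAP 13.1.5 and the Kaplan-Meier time to revert to QW (Protocol 9.3.4) follow the regimen actually received, and Table D tells the analyst to consider actual allocation. These summaries stay correctly defined; only who falls into each group can shift. The study tests no hypothesis. This too stands.

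Three stronger conclusions are tempting, and the documents do not support them:

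- A reader might infer that under 4.1 nobody can start on Q2W, or that a participant at 0 or 2 on day 1 can never become a responder. Both hold only under reading (a). The <5 criterion names no reference visit, and the nonresponder sentence permits reading (c).
- A reader might infer that SAP 6.2, which sets the default baseline as the last qualifying-study value, leaves out the needed exception. Section 6.2 refers to an Appendix 1 entry on baseline that is not in the supplied text, so this cannot be judged.
- A reader might infer that the SoA date error distorts the clinESSDAI analysis. Day 127 lies inside the SAP's week-16 window (days 2 to 141), so it does not. It could matter only for the ±2-day rule on predose pharmacokinetic samples in SAP 18, where exclusions are decided case by case.

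**Conclusion.** The conflict is real and should be fixed. As written, Section 4.1 makes the 3-point criterion unattainable on day 1 unless clinESSDAI is repeated. Under every reading of the <5 criterion, it puts a participant who fell by 3 or more points in the qualifying study but is still at ≥5 on the opposite starting regimen from the synopsis, schema and SAP figure. If the score then holds, that participant has 8 extra infusions before week 16, 12 extra before week 24, and a therapeutic-failure evaluation at week 24. For participants already below 5 on day 1, 4.1 is ambiguous rather than wrong. The glossary definition of therapeutic failure contradicts the PI-judgement rule in both documents.

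The effects fall on dosing, possible discontinuation, the composition of the regimen-based descriptive summaries, and the baseline item on responder status in SAP Section 9. The definitions of the primary safety and secondary efficacy endpoints do not use this rule. Using the extension baseline for their change scores is a separate matter and not an error.

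The 14-10-10-10 scores are an assumed illustration. The documents give no score distribution, so the number affected could be anywhere from 0 to the planned enrolment of about 30.

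**What to change.** 1. Protocol 4.1: state that both responder criteria (a fall of ≥3 points, and a change from ≥5 to <5) are measured from the baseline of the qualifying study. Delete the parenthesis that equates baseline with the final qualifying-study visit.
2. Protocol 4.1 and both Definitions of Terms: define a nonresponder simply as a participant who is not a responder. Read inclusively, the present and/or wording makes some participants both.
3. Both Definitions of Terms: define therapeutic failure as a nonresponder at week 24 or later for whom the PI, after the evaluation in 4.1, decides that treatment should stop. Add that other nonresponders continue QW.
4. SAP 3.1: name the qualifying-study baseline as the reference for responder status. Do the same in SAP 6.2, as an exception to the default baseline, unless Appendix 1 already does so.
5. SoA, as a separate correction: weeks 13 to 15 = days 92 to 106, week 16 = day 113, weeks 17 to 23 = days 120 to 162.

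The cost is a protocol amendment with ethics approval, and health-authority approval if it counts as substantial (Protocol 10.1.1), plus matching SAP text. No new visits, procedures or data are needed.

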IMP	investigational medicinal product
IRB	institutional review board
ITP	immune thrombocytopenia
IV	intravenous
IVIg	intravenous immunoglobulin
JAK	Janus kinase
MedDRA	Medical Dictionary for Regulatory Activities
MFI	Multidimensional Fatigue Inventory
NCI	National Cancer Institute
NCS	Nerve conduction studies
NSAID	non-steroidal anti-inflammatory drug
OLE	open-label extension
OSS	ocular staining score
PASS	patient acceptable symptom state
PCR	polymerase chain reaction
PD	pharmacodynamic(s)
PGA	patient global assessment
PI	principal investigator

Abbreviation	Expansion
PK	pharmacokinetic(s)
PMDA	Pharmaceuticals and Medical Devices Agency
pSS	primary Sjögren’s syndrome
PT	preferred term
QW	once weekly
Q2W	every 2 weeks
RF	rheumatoid factor
SAE	serious adverse event
SAP	statistical analysis plan
SC	subcutaneous
SCIg	subcutaneous immunoglobulin
SF-36	36-Item Short Form Survey
SFV	safety follow-up visit
SGUS	salivary gland ultrasonography
SoA	schedule of activities
SOC	system organ class
SS-A	Sjögren’s syndrome–related antigen A
SS-B	Sjögren’s syndrome–related antigen B
STAR	Sjögren’s Tool for Assessing Response
SUSAR	suspected unexpected serious adverse reaction
SWSF	stimulated whole salivary flow
TEAE	treatment-emergent adverse event
UWSF	unstimulated whole salivary flow
VAS	visual analog scale
WOCBP	women of childbearing potential

Definitions of Terms

Term	Definition
Nonresponder	Participant who does not have a reduction in ClinESSDAI score of ≥ 3 points and/or a change in score that alters their disease severity category
Responder	Participant who has a reduction in ClinESSDAI score of ≥ 3 points and/or a change in score that reclassifies their disease from moderate severity to mild severity
Therapeutic failure	Participant who are nonresponder at week 24. This participant will discontinue study treatment

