8.1. Disposition

The number of participants will be summarized for FAS. The number of participants per country and site will also be provided using the FAS. The number of participants who completed or discontinued the treatment and/or the study along with the reason for discontinuation will be summarized using the FAS.

Participant disposition and withdrawals will be presented for the FAS.

The enrollment failures will be summarized using number of participants who signed the informed consent form.

Copyright © 2009, 2010, 2012, 2016, 2018, 2019, 2021, 2024 IQVIA. All rights reserved. The contents of this document are confidential and proprietary to IQVIA Holdings Inc. and its subsidiaries. Unauthorized use, disclosure or reproduction is strictly prohibited.

Data will be tabulated at least for:

- Number of participants in each analysis sets.
- number and percentage of participants enrolled, completed, or discontinued the study.
- number and percentage of participants for each study discontinuation reason.
- number and percentage of participants discontinuing treatment but continuing study assessments.

A listing of participant disposition will be prepared to present information about treatment discontinuation and study discontinuation.

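### A participant on Q2W who is a nonresponder at week 24 meets inconsistent instructions: stop, QW with a way back to Q2W, or QW to the end of treatment

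*Protocol*

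**What the plan says.** - **Week 24 branch.** Protocol section 4.1: "If a participant is not a responder at week 24, they will be evaluated by the PI for therapeutic failure". There is no condition on current regimen. The two outcomes are "Therapeutic failure - the participant will discontinue study treatment" and "Not a therapeutic failure - the participant will continue QW dosing regimen". After the second, "ClinESSDAI will be conducted at weeks 32, 36, 40, and 44 until confirming responder status and switching to Q2W dosing regimen". The synopsis, the schema note, footnote o of the Schedule of Activities and SAP section 3.1 carry the same scheme.
- **Definitions tables.** The protocol defines therapeutic failure as "Participant who are nonresponder at week 24. This participant will discontinue study treatment". The SAP's table says the same. Neither mentions the investigator's judgement or the regimen.
- **Reversion rule.** If the participant or investigator "consider there to be a reduction in therapeutic effect once the patient has switched to Q2W, the participant will return for an unscheduled visit". If clinESSDAI has risen by at least 3 points, or disease has gone from mild to moderate, "the participant will revert to QW dosing regimen and will remain on this dose regimen for the remainder of the treatment period". Footnote p of the Schedule of Activities repeats this. Neither place names the score from which the rise is measured.
- **General rule.** Section 4.1 also gives nonresponders weekly infusions until they respond, and section 6.3 assigns Q2W or QW by responder status.
- **SAP Table D (section 11).** A participant who starts on Q2W on day 1 and becomes a nonresponder at a listed visit, week 24 included, is classed as switching to QW and ending the study on it.

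**The concern.** The week 24 branch is written as if every nonresponder were on QW. Someone on Q2W has no weekly regimen to continue, and three other pieces of text also bear on that person with different results. Two sites could handle identical participants differently, one stopping drug and the other giving weekly infusions, and each could point to the documents.

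Protocol section 4.3 gives the purpose of Q2W as learning whether less frequent dosing maintains efficacy. The summaries that bear on this are the Kaplan-Meier time to reverting to QW (protocol section 9.3.4), the subgroup switching back from Q2W to QW (SAP section 13.1.5) and the Table D classes. All depend on which instruction was followed. A therapeutic-failure category that does not show the regimen would also mix failure on weekly dosing with loss of response after the frequency was halved. A participant who is stopped at week 24 contributes up to 48 − 24 = 24 fewer weeks of treatment-period data to the primary safety objective.

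**Working it through.** No figure in the plan bears on this point, so the check sets the rules side by side and then runs scores through them.

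**Can the case arise?** Yes. Switching to Q2W can occur on day 1 or at week 16, and week 24 clinESSDAI is scheduled for all; footnote k restricts only weeks 32, 36, 40 and 44. Section 4.1 describes the reference baseline as the final visit of the qualifying study, which footnote a says coincides with the OLE baseline. On that reading no reduction is possible on day 1. The synopsis and schema use the qualifying study's baseline. Week 16 switching is enough for the case to exist on either reading.

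**Rules side by side**

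| Source | Covers | Action | Return to Q2W later? |
|---|---|---|---|
| Section 4.1, week 24 branch | Any week 24 nonresponder | Investigator judges: stop, or stay on QW | Yes, on confirmed response at weeks 32–44 |
| Definitions tables (protocol, SAP) | Every week 24 nonresponder | Stop | Not applicable |
| Reversion rule | On Q2W, unscheduled visit, worsening criterion met | QW | No |
| General rule (sections 4.1, 6.3) | Nonresponders, any regimen | QW | Yes, once a responder |
| SAP Table D | Day 1 Q2W starter, nonresponder at a listed visit | Ends on QW | Not in that class |

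**Scores run through the rules.** Let B be the reference score, S the score while responding on Q2W and W the week 24 score.
- Responder at score x: B − x ≥ 3, or B ≥ 5 and x < 5. Nonresponder is taken as the complement.
- Reversion: W − S ≥ 3, or S < 5 and W ≥ 5. Measuring the rise from S, and applying the criterion at a scheduled visit, are assumptions.

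| B, S, W | On Q2W by S? | Week 24 status | Reversion criterion |
|---|---|---|---|
| 10, 6, 9 | 10 − 6 = 4, yes | 10 − 9 = 1, nonresponder | 9 − 6 = 3, met |
| 7, 4, 6 | 7 − 4 = 3, yes | 7 − 6 = 1 and 6 ≥ 5, nonresponder | mild to moderate, met |
| 10, 6, 8 | 10 − 6 = 4, yes | 10 − 8 = 2, nonresponder | 8 − 6 = 2, not met |
| 20, 10, 14 | 20 − 10 = 10, yes | 20 − 14 = 6, responder | 14 − 10 = 4, met |

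The first row changes with the reference score: measured from B, 9 − 10 = −1, which is no rise at all. The fourth row shows that the two criteria are different tests, since reversion can be met by someone still classed as a responder.

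Enumerating all whole-number triples from 0 to 30 under the same assumptions gives 4,867 in which response is lost at week 24 and reversion is met, 73 in which response is lost and reversion is not met (rises of 1 or 2 points), and 2,998 in which reversion is met by a continuing responder. These count score combinations and are not probabilities.

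**Number affected.** The documents give no rates. Assume 9 to 18 of about 30 are on Q2W before week 24, and 10% to 30% of those are nonresponders at week 24:
- low: 9 × 0.10 = 0.9; high: 18 × 0.30 = 5.4; so about 1 to 5 people;
- one person is 1/30 = 3.3% of the study, and 1/18 = 5.6% to 1/9 = 11.1% of the Q2W group.

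**The case against.** The strongest reply is that section 4.1, read in order, is workable. Stopping requires the investigator to judge therapeutic failure, and otherwise the participant is on QW, which is the same immediate regimen that reversion gives. The general rule supplies QW for a nonresponder whatever the current regimen. The study is descriptive, with no hypothesis and no inferential use, and few people are likely to be involved.

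Much of this stands, and it rules out three stronger readings.
- A reader might infer that everyone in this position is told both to stop and to revert. Section 4.1 does not make stopping automatic. Only the Definitions tables do, and they conflict with section 4.1 for participants on QW throughout as well. Reversion is worded for an unscheduled visit, with no stated reference score, so the overlap in the 10, 6, 9 example is possible rather than certain.
- A reader might infer that no rule reaches a participant with a small rise, such as 10, 6, 8. The general rule does, if failure is not declared.
- A reader might infer that Q2W will look better maintained than it is. That depends on whether a failure stop while on Q2W is an event or is censored. Protocol section 9.3.4 does not say, and the SAP's exploratory sections are redacted.

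What the reply does not remove: the Definitions tables still say stop with no judgement. The week 24 branch and the general rule allow Q2W to resume while reversion forbids it. The SAP itself is unsettled on whether reversion belongs to unscheduled visits, because Table D counts scheduled visits and its note says worsening is recorded at weeks 24, 32, 40 and 44 as well as unscheduled ones.

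**Conclusion.** The point holds as an inconsistency in the stated rules. For a participant on Q2W who is a nonresponder at the scheduled week 24 assessment, the documents do not settle whether treatment stops or becomes weekly, nor whether a return to Q2W is then allowed. The general nonresponder rule fills only part of the gap. The effect falls on who stays on drug, on the Table D classes and switch-back subgroup, and on the time-to-reversion analysis.

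Its size is unknown. The figure of 1 to 5 participants rests wholly on the assumed rates above. With about 30 participants, even one or two cases would show in the Q2W summaries, but no direction of bias can be claimed from the visible text. It should be corrected because stated rules contradict each other on treatment and classification.

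**What to change.** 1. **Reconcile the text.** Bring protocol section 4.1, the synopsis, the schema note, footnotes o and p, both Definitions tables, SAP section 3.1 and Table D to one rule for a participant who is on Q2W when found to be a nonresponder at week 24. Which rule is for the sponsor's clinical team. The text should say whether the reversion criterion applies at scheduled visits, from which score the 3-point rise is measured, and whether a return to Q2W is possible afterwards. Align the Definitions tables with section 4.1 on the investigator's role for QW participants too.
2. **SAP section 8.1.** Split therapeutic failure, as a reason for discontinuing treatment, by the regimen in force at the decision. The bullet giving "number and percentage of participants for each study discontinuation reason" concerns leaving the study and is not the right place; the same section separately summarises treatment discontinuation with its reason.
3. **Time-to-reversion analysis (protocol section 9.3.4).** State how a therapeutic-failure stop while on Q2W is handled. Count it as loss of Q2W maintenance, or show that as a sensitivity analysis, rather than treating it as a non-event.

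Cost: wording changes in the listed places, one extra table split and at most one added analysis. No new data are needed, since the date and dose of every infusion are already recorded.
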